#### **8.4. Exploratory Efficacy Endpoint**

Observed values and changes from baseline for each scheduled post-baseline visit will be summarized descriptively for the following endpoints:

- Gaucher disease severity score (GD-DS3)
- Bone marrow burden score measured by MRI
- Bone mineral density measured by DEXA:
  - Z-score and T-score at lumbar spine and hip (left and right)
- Fatigue measured by Functional Assessment of Chronic Illness Therapy - Fatigue score (FACIT-Fatigue)
- Gaucher disease activity biomarkers: chitotriosidase
- Bone biomarkers: bsALP, osteocalcin
- Lung disease measured by chest x-ray and pulmonary function tests
- GCase concentration
- HRQoL measured by SF-36 domains

The above summaries will be by study part, dose cohort, and overall.

Additionally, chitotriosidase activity levels will be plotted by-participant over time.

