- GCase concentration
- Genotyping (GBA1 and CHIT1); only if previously not determined
- Chitotriosidase, CCL18, bsALP, osteocalcin (at both Screening visits)

Alanine amino transferase (ALT) levels will guide treatment for breakthrough transaminitis during the study and alcohol intake can cause ALT levels to rise, making it difficult to determine whether transaminitis is alcohol or vector associated. As such, participants will be advised to moderate their intake of alcohol as described in Section 9.3.2.

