## List of Abbreviations

AAVS3	Adeno-associated viral vector serotype S3
AE	Adverse Event
AESI	Adverse Events of Special Interest
ALT	Alanine aminotransferase
APTT	Activated partial thromboplastin time
AR	Adverse reaction
AST	Aspartate aminotransferase
ATC	Anatomical Therapeutic Chemical
AUC	Area under curve
BLQ	Below the Limit of Quantification
BPI-SF	Brief Pain Inventory- Short Form
bsALP	Bone specific Alkaline Phosphatase
CHIT1	Gene encoding for Chitotriosidase
CMV	Cytomegalovirus
DEXA	Dual energy x-ray absorptiometry
DLT	Dose-limiting toxicity
DMC	Data monitoring committee
ECG	Electrocardiogram
eCRF	Electronic case report form
EOS	End of study
ERT	Enzyme replacement therapy
EU CTR	European Union Clinical Trial Regulation
FACIT-Fatigue	Functional assessment of chronic illness therapy fatigue scale
GBA1	Gene encoding for $\beta$ -glucocerebrosidase
GCase	Glucocerebrosidase
GD-DS3	Gaucher Disease severity score
HRQoL	Health-related quality of life
ICF	Informed Consent Form
ICH	International Conference on Harmonisation
INR	International normalized ratio
IV	Intravenous(ly)
LFT	Liver function test
LOD	Limit of Detection
LOQ	Limit of Quantification
Lyso-Gb1	Glucosylsphingosine
MCS	Mental Component Summary Score
MedDRA	Medical Dictionary for Regulatory Activities
MRI	Magnetic resonance imaging
MTD	Maximum Tolerated Dose
NCI	National Cancer Institute
NIMP	Non-investigational medicinal product
PCR	Polymerase chain reaction
PCS	Physical Component Summary Score
PD	Pharmacodynamic
PK	Pharmacokinetic
SAE	Serious Adverse Event
SAP	Statistical analysis plan
SAR	Serious adverse reaction
SF-36	Short Form Health Survey
SOC	System organ class
SRT	Substrate Reduction Therapy
SUSAR	Suspected, unexpected, serious adverse reaction
TEAE	Treatment emergent adverse event
ULOQ	Upper Limit of Quantification
vg	Vector genomes

WHO

World Health Organization

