## **4. General Statistical Considerations**

All study data collected will be presented in data listings, and all relevant data will be tabulated and summarized by study part, dose cohort, and overall, unless stated otherwise.

Continuous data will be described using descriptive statistics (i.e., n, mean, standard deviation, median, minimum, and maximum). Categorical data will be described using the count and percentage in each category. For the summary statistics of all numerical variables unless otherwise specified, minimum and maximum will be displayed to the same level of precision as reported. Mean and median will be displayed to one level of precision greater than the data collected. Standard deviation, standard error, and confidence intervals will be displayed to two levels of precision greater than the data collected.

Missing data will not be imputed. All analyses will be based on observed cases for the safety population unless specified otherwise.

Clinical laboratory and PK results that are below the lower limit of quantification (BLQ/LOQ), below the limit of detection (LOD), above the upper limit of quantification (ULOQ) or missing will be displayed as such in the data listings.

To calculate descriptive statistics and PK parameters, all BLQ, LOQ and LOD results will be treated as half of the BLQ/LOQ/LOD values whereas all ULOQ values will be treated as the ULOQ values as applicable.

The end of the study will be defined as the last visit by the last participant. All participants will be followed up for at least 5 years in a separate long-term follow-up study.

Unless specified otherwise, baseline will be defined as the last non-missing measurement prior to the infusion of IMP.

Change from baseline is defined as: post-baseline value – baseline value.

Study Day 1 is the calendar day of the IMP infusion. Subsequent study days are calculated as the date of assessment/event – date of infusion + 1. Pre-infusion study days are calculated as date of assessment/event – date of infusion. There is no Study Day 0.

All data are summarized based on the visit name collected on the eCRF page.

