### **4.4.2. Safety Set**

The Safety Set will include all participants who received any dose of FLT201. This population will be used to report both Parts 1 and 2. All data summaries will use the Safety Set, unless otherwise specified.

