### **8. Efficacy Analysis**

Summaries and analysis of efficacy endpoints will be performed using the Safety Set unless otherwise specified.

Primary endpoints and secondary efficacy endpoints descriptive summaries will also be used to support the clinical trial results summary part of the EU CTR reporting.

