#### **14. Changes in the Planned Analysis**

1. Section 8.4: Analysis of exploratory endpoint Gaucher disease activity biomarkers (CCL18) is omitted from this SAP as data is not collected.
2. Section 9.2.3: Analysis of safety endpoint, clinical laboratory evaluations urinalysis is omitted from this SAP as research urine samples are not available for analysis.
3. Section 9.1.8: Adverse Events Leading to Study Discontinuation is omitted from this SAP as data is not collected.
4. In the study protocol, an interim analysis is planned but will not be performed.

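### SAP 8.4 averages chitotriosidase change over every dosed participant without using the CHIT1 genotype it collects, so any participant unable to make the enzyme would dilute a cohort mean of two or three

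*SAP*

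**What the plan says.** SAP 8.4 includes "Gaucher disease activity biomarkers: chitotriosidase" in the exploratory efficacy endpoints, with observed values and change from baseline tabulated at each scheduled visit. On grouping it says "The above summaries will be by study part, dose cohort, and overall". A by-participant plot of chitotriosidase over time is also planned.

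The analysis population is set in SAP 8: "Summaries and analysis of efficacy endpoints will be performed using the Safety Set unless otherwise specified". SAP 4.4.2 defines that set: "The Safety Set will include all participants who received any dose of FLT201". No inclusion or exclusion criterion in Protocol 9.1 or 9.2 concerns CHIT1.

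The SAP abbreviation list explains CHIT1 as "Gene encoding for Chitotriosidase". Protocol 12.1.1 has it determined at screening: "Genotyping (GBA1 and CHIT1); only if previously not determined". Its only stated use in the SAP is in section 6.2, as a baseline disease characteristic that is summarised and listed.

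Two general rules in SAP 4 bear on the result. Change is the absolute difference between the post-baseline and baseline values. For descriptive statistics, "all BLQ, LOQ and LOD results will be treated as half of the BLQ/LOQ/LOD values".

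The protocol paired chitotriosidase with a second disease-activity biomarker, CCL18. SAP 14 removes it: "Analysis of exploratory endpoint Gaucher disease activity biomarkers (CCL18) is omitted from this SAP as data is not collected".

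**The concern.** A participant with no working copy of the gene cannot produce the enzyme being measured. That person's chitotriosidase result says nothing about disease response, yet the planned tables count it in n and in the mean as an ordinary observation of no change. The genotype that would identify the person is already collected, but nothing in the SAP connects it to this analysis.

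The effect is largest at dose-cohort level, where the groups are smallest. A cohort could appear to show a weaker biomarker change because of who was enrolled in it rather than because of the dose. With CCL18 gone, such a participant also has no informative marker left under the disease-activity biomarker item.

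**Working it through.** The documents state no figure for chitotriosidase, so there is nothing to reproduce. The check applies the SAP's own rules.

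**Inputs**
- Population: all dosed participants (SAP 8 and 4.4.2).
- Change: post-baseline minus baseline (SAP 4).
- Results below a limit: half that limit (SAP 4). The rule covers clinical laboratory results, and Protocol Table 1 lists chitotriosidase under central laboratory tests.
- Cohort size: at least 2, with a possible third. A cohort of 1 can arise under the GCase rule (Protocol 13.3.1 and 13.3.1.2).
- Planned totals: about 12 in Part 1 and 18 over both parts (Protocol synopsis).
- Frequency of participants with no functional copy: not in the documents. Assumed range 1% to 10%.

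**Step 1: change for a non-producer.** If both results are below the same limit L, change = L/2 − L/2 = 0 for any L.

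**Step 2: effect on the mean.** With one zero among n participants, the mean is (n − 1)/n times the mean change in the others. Taking a change of −100 units in each producer for illustration:

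| n | Mean as planned | Mean, producers only | Reduction |
|---|---|---|---|
| 2 | −50.0 | −100 | 50% |
| 3 | −66.7 | −100 | 33% |
| 12 | −91.7 | −100 | 8% |
| 18 | −94.4 | −100 | 6% |

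A cohort of 1 would show only the 0.

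**Step 3: does the median help?** At n=2 it does not, because the median equals the mean. At n=3 it helps in part: with changes of −120, −80 and 0, the mean is −66.7 and the median −80, against −100 for both without the non-producer.

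**Step 4: how likely is it?** The chance of at least one non-producer is 1 − (1 − p)^n.

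| Assumed p | n=2 | n=3 | n=12 | n=18 |
|---|---|---|---|---|
| 1% | 2.0% | 3.0% | 11.4% | 16.5% |
| 3% | 5.9% | 8.7% | 30.6% | 42.2% |
| 5% | 9.8% | 14.3% | 46.0% | 60.3% |
| 10% | 19.0% | 27.1% | 71.8% | 85.0% |

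For any one cohort the event is fairly unlikely over this range. For the study as a whole it is a realistic possibility except near the bottom of the range.

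**The case against.** The strongest reply is that this is a contingency in an exploratory endpoint. The documents do not say that any participant lacks functional CHIT1, and they give no frequency. All analysis is descriptive. Chitotriosidase has no responder definition and no test, and the specific dose-escalation rules (Protocol 13.3.1.1 to 13.3.1.3) rest on DLTs, GCase activity and the NOAEL. The only dose model in the SAP is the GCase power model (10.4). The SAP also reports median, minimum and maximum, lists all data and plots chitotriosidase by participant. With two or three people in a cohort, a flat line would be noticed and could be matched by hand to the genotype listing.

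Most of this stands, and it limits the importance of the point. Two things remain. The displays expose a flat line but leave the cohort and overall tables unchanged. A flat line also does not explain itself: Part 1 participants must have started ERT or SRT at least two years before dosing (Protocol 9.1), so low, stable values could reflect treated disease as well as inability to make the enzyme. Genotype can help separate these, and the SAP does not bring it to this analysis.

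A reader might infer from the loss of CCL18 that evidence on disease activity now rests on chitotriosidase alone. It does not: lyso-Gb1 is a secondary endpoint, tabulated and plotted by participant (SAP 8.3).

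**Conclusion.** The point holds as a conditional weakness of modest importance. If a participant with no functional CHIT1 copy is enrolled, the stated rules produce a cohort mean change of 1/2 (n=2) or 2/3 (n=3) of that in the other members, and an overall mean about 6% to 8% too small (n=18 to 12).

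This rests on three assumptions. First, lacking a functional copy means no measurable enzyme, which is an inference from what the gene encodes. Second, baseline and follow-up fall below the same limit; with a noisy value above it, or a different limit, the change would be near 0 rather than exactly 0. Third, such a participant is enrolled at all, for which the 1% to 10% range is assumed.

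A reader might go further and infer that the chitotriosidase tables are already wrong, that lack of response will be declared, or that dose decisions are affected. The documents support none of these: they report no such participant, define no response and attach no rule specific to this biomarker. Nor do they give a basis for quantifying any effect of carrying a single functional copy.

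**What to change.** In SAP 8.4, pre-specify that the chitotriosidase summary tables are restricted to participants whose CHIT1 genotype allows enzyme production, with the evaluable n shown beside the number dosed. Keep every participant in the listing and in the by-participant plot, and mark CHIT1 status on both. Base the restriction on genotype and not on low values, so that a producer with below-limit results stays in. Percent change could be added but is optional.

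Because the criterion is a fixed baseline characteristic, the restriction does not select on outcome. Writing it down in advance matters in an open-label study, where an exclusion made after a flat line has been seen would look data-driven.

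The cost is a short SAP amendment, a lower n in one exploratory table, and a classification of CHIT1 genotypes by functional status before database lock, including a rule for variants of uncertain effect. No new data are needed.

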##### **8.4.1. Pain measured by Brief Pain Inventory - Short Form (BPI-SF)**

The two pain domains (pain severity and pain interference) scores measured by BPI-SF questionnaire will be calculated as the average daily pain scores during the 7 days immediately following each screening visit (rounding to nearest whole number is not permitted).

Post-infusion two pain domains (pain severity and pain interference) values will be computed similarly, i.e., as an average of 7 daily values. The computation will be performed for Weeks 4, 12, 24 and 38/EOS.

The baseline will be defined as the observed BPI-SF pain domain score for pre-infusion (Day -1) visit. If pre-infusion (Day -1) visit score is missing, the weekly average of the latest screening visit pain domain score recorded during the 7 days following the screening visit (and prior to infusion) will be used as the baseline.

A summary table by study part, dose cohort, and overall will be provided for BPI-SF each pain score averages and changes from baseline for each scheduled post-baseline visit.

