- B If a site is not able to administer FLT201 the Sponsor will attempt to identify an alternative site for the infusion week only.
- C Height (screening only) and weight will also be measured.
- D Vital signs include pulse, blood pressure, respiratory rate, and temperature.
- E Participants will complete BPI-SF questionnaire once a day covering the 7 days following each screening visit, and then for 7 consecutive days, on each occasion commencing at the start of Weeks 4, 12, 24 and 37 post-treatment (week prior to the 38-week visit). Study sites will contact participants at the beginning of Week 37 to remind them to complete the questionnaires during Week 38.
- F Participants will complete the FACIT-Fatigue questionnaires at the end of each week during the screening period, and then at the end of Weeks 4, 12, 24, and 37 post treatment.
- G A weight-based tapering immunosuppressive regimen will be initiated at the Week 3 visit. Cohort 1 may not require immunosuppression. For details see the pharmacy manual.
- H Serum pregnancy test performed only at Week 1 to EOS and unscheduled visits if the urine pregnancy test is positive.
- I Testing to be performed twice weekly (including the testing as part of the scheduled study visit), initially commencing at Week 1 and concluding at the end of Week 9 and later commencing at Week 28 and concluding at the end of Week 38/EOS. The tests should be as evenly spaced through the week as possible, for example: Monday and Thursday, or Tuesday and Friday.
- J Testing to be performed three times weekly (including the testing as part of the scheduled study visit), commencing at Week 10 and concluding at the end of Week 27. The tests should be as evenly spaced through the week as possible, for example Monday, Wednesday, and Friday.
- K Local testing. Weekly CMV PCR testing for the duration the participant is taking tacrolimus in the immunosuppressant regimen. Tests should be undertaken to coincide with use of tacrolimus if outside of the prophylactic regimen. CMV IgG testing followed by CMV PCR. CMV PCR only indicated for a positive CMV IgG.
- L Local testing. Tacrolimus levels should be tested twice weekly until levels are in the therapeutic range and weekly thereafter for the duration the participant is taking tacrolimus in the immunosuppressant regimen. Tests should be undertaken to coincide with use of tacrolimus if outside of the prophylactic regimen.

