12.1 Study Schedule

12.1.1 Screening

The following study-specific procedures will be carried out after the informed consent form (ICF) is signed to assess the participant's eligibility. Screening evaluations will be performed at the study site. Screening evaluations may take place over a number of visits, as necessary, to complete all assessments. A window of up to 16 weeks (from initial consent to Day 0) is allowed for screening. At least two screening visits will be performed to complete all necessary assessments. Participants may be rescreened should this time window elapse.

- Demography and medical history
- Prior and concomitant medication (at both screening visits)
- Gaucher disease history (including ERT/SRT history)
- Gaucher disease severity (GD-DS3) (within 4 weeks of dosing only)
- Physical examination including measurement of the participant's height and weight.
- Vital signs (pulse, blood pressure, respiration rate, and temperature)
- 12-lead ECG
- AEs during the screening period from the time of initial consent
- Abdominal and bone MRI (within 4 weeks of dosing only)
- DEXA Z-score and T-score; lumbar spine and hip (within 4 weeks of dosing only)
- Participants will be asked to complete an electronic diary, answering questions relating to:
 - BPI-SF questionnaire: pain during the last 24 hours – daily over the 7 days following each Screening visit
 - FACIT Fatigue during the 7 days prior to each Screening visit

Participants will be issued with instructions on electronic diary completion.

- HRQoL evaluated using the SF-36 questionnaire (within 4 weeks of dosing only)
- Chest x-ray and pulmonary function tests (within 4 weeks of dosing only)
- Serum pregnancy test for female participants (local laboratory analysis) (at both screening visits)
- Blood samples to evaluate (central laboratory analysis) (Screening laboratory assessments can be repeated on one further occasion if the initial test result falls outside the protocol eligibility criteria):
 - AAVS3 immune response. Note: A blood sample drawn within 6 weeks of dosing must be confirmed as negative for AAVS3 neutralising antibodies before a participant can be considered for dosing. It is acceptable to take repeat samples during the screening period, as necessary.
 - Haematology and chemistry (including LFTs and hs troponin-T, vitamin D, Fe²⁺, and vitamin B12) (at both Screening visits), and viral serology
 - Lyso-Gb1
 - GCase immune response

- GCase activity level

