12.1.3 Pre-infusion (Day -1)

Day -1 assessments may be conducted as early as Day -3 for logistical reasons, if required:

- Physical examination (including confirmation of weight).
- Vital signs (pulse, blood pressure, respiration rate, and temperature).
- 12-lead ECG.
- AE and concomitant medication status.
- Urine pregnancy test (serum confirmation if positive urine test)
- SARS-CoV-2 (COVID-19) test
- LFTs including albumin, alkaline phosphatase, direct/indirect and total bilirubin, ALT, and AST (local laboratory analysis)
- Blood samples to evaluate (central laboratory analysis):
 - Haematology, chemistry (including hs troponin-T and LFTs)
 - GCase immune response
 - GCase concentration

- AAVS3 immune response (to retrospectively check status of anti-AAVS3 neutralising antibodies immediately prior to dosing)
 - Research plasma sample
- Plasma, saliva, urine, stool, (and semen, male participants only) samples for PCR of vg.
- BPI-SF and FACIT-Fatigue questionnaires.

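### The BPI-SF change score sets a single Day -1 rating against 7-day post-dose means, although matching 7-day screening diaries are scheduled, scored and kept only as a fallback

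*SAP*

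**What the plan says.** SAP 8.4.1 covers two BPI-SF domains, pain severity and pain interference. It treats three periods as follows.

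- **Screening.** Domain scores are "calculated as the average daily pain scores during the 7 days immediately following each screening visit".
- **Post-dose.** The "values will be computed similarly, i.e., as an average of 7 daily values". On timing: "The computation will be performed for Weeks 4, 12, 24 and 38/EOS".
- **Baseline.** "The baseline will be defined as the observed BPI-SF pain domain score for pre-infusion (Day -1) visit". The screening diary enters only as a substitute: "If pre-infusion (Day -1) visit score is missing, the weekly average of the latest screening visit pain domain score" is used instead.

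The protocol supplies the data for both kinds of baseline. Table 1, footnote E: "Participants will complete BPI-SF questionnaire once a day covering the 7 days following each screening visit". At least two screening visits are expected (footnote A). Section 12.1.1 gives the recall period: "BPI-SF questionnaire: pain during the last 24 hours". Section 12.1.3 lists the "BPI-SF and FACIT-Fatigue questionnaires" among the Day -1 assessments and allows those assessments to be done as early as Day -3.

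Neither document explains why the single rating ranks above the weekly average. SAP 8.4.1 sets no minimum number of completed days for a weekly mean, and SAP Section 4 says that missing data are not imputed.

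**The concern.** A change from baseline is easiest to read when both ends are measured in the same way. Here one end is a single day and the other averages a week. The single day carries its full day-to-day variation into every change score for that participant, at all four post-dose time points.

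The fallback adds a second problem. A participant with a missing Day -1 score gets a baseline averaged over up to 7 days, and the next participant gets a one-day baseline. Both are then summarised in the same row.

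Cohorts are planned with at least two participants and a possible third, so one unusually good or bad day in one person can visibly move a cohort mean. Because the analysis is descriptive, the tabulated means and SDs are the result itself.

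**Working it through.** The documents state no variance, SD or sample size for BPI-SF, so there is no figure of the plan's own to reproduce. The check compares the error variance of the change under the two possible baselines.

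**Inputs from the documents**
- Baseline under the plan: 1 daily rating (SAP 8.4.1).
- Alternative baseline: mean of 7 daily ratings (SAP 8.4.1; Protocol Table 1, footnote E).
- Post-dose value: mean of 7 daily ratings (SAP 8.4.1).
- One questionnaire covers 24 hours, so it counts as one daily rating (Protocol 12.1.1).

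**Assumptions, not in the documents**
- Daily error variance w, the same before and after dosing.
- Errors in the baseline period are independent of those in the post-dose week.
- No true drift in pain between the screening diary and infusion.
- Day-to-day correlation ρ within a week, varied below.

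**Formula**

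Error variance of the change = w × [V(baseline days) + V(7)], where V(m) is the variance of an m-day mean in units of w and V(1) = 1. The ratio of the plan to a matched 7-day baseline is (1 + V(7)) / (2 × V(7)). It does not depend on w, but it does depend on ρ.

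**Independent days**

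V(7) = 1/7.
- Plan: 1 + 1/7 = 1.143 w, SD 1.069 √w.
- Matched: 1/7 + 1/7 = 0.286 w, SD 0.535 √w.
- Variance ratio (8/7)/(2/7) = 4.0; SD ratio 2.0.
- SE of a cohort mean change with 3 participants: √(1.143/3) = 0.617 against √(0.286/3) = 0.309, in daily SDs.

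**Correlated days**

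With equal correlation within the week, V(7) = (1 + 6ρ)/7. With first-order autoregressive correlation, V(7) is the average of ρ^|i−j| over the 7 × 7 pairs of days.

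| Structure | ρ | V(7) | Variance ratio | SD ratio |
|---|---|---|---|---|
| Independent | 0 | 0.143 | 4.00 | 2.00 |
| Autoregressive | 0.2 | 0.202 | 2.98 | 1.73 |
| Autoregressive | 0.5 | 0.348 | 1.94 | 1.39 |
| Autoregressive | 0.8 | 0.641 | 1.28 | 1.13 |
| Equal | 0.2 | 0.314 | 2.09 | 1.45 |
| Equal | 0.5 | 0.571 | 1.38 | 1.17 |
| Equal | 0.8 | 0.829 | 1.10 | 1.05 |

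**Dilution in the reported SD**

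If true change differs between participants with variance τ², the ratio of total variances with independent days is (τ² + 8/7)/(τ² + 2/7), with τ² in units of w. For τ² = 0.5, 1 and 2 it is 2.09, 1.67 and 1.38.

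**Incomplete baseline diaries**

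With independent days and a full post-dose week, 4 completed baseline days give (8/7)/(1/4 + 1/7) = 2.91, and 5 give (8/7)/(1/5 + 1/7) = 3.33. A partly completed diary still gives the more precise baseline in this case.

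**The case against.** The plan's rule can be defended. SAP Section 4 defines baseline generally as the last non-missing value before infusion, and Day -1 fits that. It is 1 to 3 days before dosing. Screen 2 is at -3 weeks ± 1 week, so its diary lies about 1 to 4 weeks before. Precision is traded against proximity, and the variance formula ignores any drift in that gap. This stands as a real downside. It is softened in Part 1, where inclusion criterion 6 requires no change in regimen for the prior 3 months and Protocol 8.1 keeps ERT/SRT going past dosing. Part 2 participants are untreated, so that argument does not extend to them.

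It also stands that the stakes are low. BPI-SF is one of many exploratory endpoints, no test is planned, and the escalation rules in Protocol 13.3.1 rest on DLTs, GCase activity and the NOAEL. The screening averages are derived and the data listed, so a reader could rebuild the other baseline.

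Three stronger readings are tempting but unsupported:

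- A reader might infer that the plan quadruples the noise. The factor 4 is a ratio of error variances that needs independent days and complete diaries. In SD it is a doubling, and positive correlation shrinks it.
- A reader might infer that Day -1 is distorted by travel or anticipation and so biases the change. Nothing in the documents shows an effect on pain, some participants attend their own site, and the visit may be as early as Day -3. Unless Day -1 is atypical, the mismatch adds noise without biasing the mean change.
- A reader might infer that reversing the order of preference ends the mixing of baselines. It does not if Day -1 remains the fallback. The diary is scheduled for everyone, but its completeness is unknown.

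**Conclusion.** The point holds as a matter of precision and comparability. Every BPI-SF change in the plan subtracts a one-day value from a weekly mean, while a matching weekly baseline is already scheduled and scored. The Day -1 baseline is the noisier one in every scenario computed. How much noisier depends on a correlation that the documents do not give: from 4 times the error variance at independence down to about 1.1 times at strong equal correlation. The ratio in the reported SD will be smaller still if participants truly differ in their change.

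These figures rest on equal daily variance before and after dosing, independent baseline and post-dose weeks, and no drift before infusion. The change is worth making because it is cheap. It does not affect the primary endpoint or the escalation rules, and with cohorts of two or three and no control group neither baseline would support a firm conclusion on pain.

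**What to change.** Replace the baseline paragraph in SAP 8.4.1 with the following rules:

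1. For each domain, baseline is the mean of the daily scores in the 7 days after the last screening visit before infusion, using pre-infusion days only.
2. State a minimum number of completed days and apply it to every weekly mean, before and after dosing. Four of 7 is an example; the documents give no figure.
3. If the minimum is not met, use the Day -1 score and flag that participant in the table and listing, so that any mixing is visible.
4. Show change from Day -1 as a sensitivity summary.

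The cost is one SAP paragraph, one flag and one additional summary, with no new data. The price is a baseline about 1 to 4 weeks before infusion instead of 1 to 3 days. The sensitivity summary shows whether that gap matters.
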